Statistical Considerations:	
The following statistical analyses are planned:
 
 • Odds ratio of antibiotic prescription between 2 groups as well as the difference in proportion of patients prescribed an antibiotic by day 28 using logistic regression corrected for variation at the GP level (generalized linear mixed effect) • Difference between the mean number of days with restricted activities by day 7 using linear mixed effect regression • Difference between the mean number of medical consultations by day 28 using linear mixed effect regression • Odds ratio of the risk of adverse outcomes between 2 groups as well as the difference in proportion of patients with adverse outcomes and clinical failure using logistic regression corrected for variation at the GP level (generalized linear mixed effect) • Difference between the mean daily symptom scores measured in the different arms. The effects of the interventions on recovery will be studied by comparing the slopes of symptom scores over time between arms • Difference in the mean duration of total time spent in the practice using linear mixed effect regression • Difference in levels of satisfaction of providers and patients between arms • Difference in the mean cost per arm using linear mixed effect regression • Diagnostic performance of: 
 ◦ individual host biomarker(s) based on crude positive and negative likelihood ratios, and on the area under the curve of receiver operator characteristic (ROC) curves, to predict the development of a serious adverse outcome, a clinical failure, or the presence of pneumonia ◦ combined biomarkers based on sensitivity and specificity generated by classification and regression trees (CART) analyses, to predict the development of a serious adverse outcome, a clinical failure, or the presence of pneumonia
GCP Statement:	This study will be conducted in compliance with the protocol, the current version of the Declaration of Helsinki, the ICH-GCP as well as all national legal and regulatory requirements.

ABBREVIATIONS

ARI	Acute Respiratory tract Infection
ASR	Annual Safety Report
CAP	Community Acquired Pneumonia
CEC	Competent Ethics Committee
CHUV	Centre Hospitalier Universitaire Vaudois
COPD	Chronic Obstructive Pulmonary Disease
CRP	C-reactive protein
CT	Computerized Tomography
CTU	Clinical Trials Unit
CXR	Chest X-ray
eCRF	Electronic Case Report Form
FOPH	Federal Office of Public Health

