11.1 Hypothesis

The null hypothesis is that there is no difference in the proportion of antibiotic prescription in patients enrolled in the different arms of the trial.

The alternative hypothesis is that combined use of POCT procalcitonin testing with lung ultrasound leads to significant reduction in antibiotic use with no difference in terms of clinical outcome, duration of the episode, activities restrictions and adverse outcomes.

A reduction of at least 15% in the proportion of patients treated with antibiotics by day 28 is expected as below this threshold, the intervention would be considered as no having a sufficient impact to warrant its implementation at larger scale, at least in its present format.

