11.2 Determination of Sample Size

The sample size was calculated to assess a decrease in antibiotic prescription of at least 15% between the UltraPro and the PCT arms as well as 15% between the PCT arm and usual care.

The proportion of patients receiving antibiotics with the usual care is estimated to be around 60% and to decrease to 45% using PCT and to 30% combining PCT and ultrasound. These numbers have been extrapolated from the subgroup of patients with LRTI in a study at primary care level in the Netherlands [3].

A study sample of 14 GPs and 15 patients per GP in each arm (210 patients per arm and a total of 630 patients) gives a power of 80% to detect a decrease in antibiotic prescription from 60% (usual care) to 45% (PCT), and from 45% (PCT) to 30% (UltraPro), with 5% level of significance, when adjusting for clustering at practice level (intracluster coefficient 0.06) [3]. This sample size guarantees a power of 80% to prove non-inferiority in terms of duration of activities restriction (non-inferiority margin=1 day, standard deviation=4 days) as well as of composite adverse outcome (probability in the “usual care” arm 0.05 with a non-inferiority margin of 0.02). Simulations used to determine the sample size are shown in the following figures.

[figure not shown]

Figure 4: Statistical simulations used to determine sample size

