11.4 Planned Analyses

Datasets to be analysed, analysis populations

The analysis will be performed in intention to treat (pragmatic trial). The analysis population will comprise all patients included by the randomised GPs. The primary analysis will include all patients enrolled in the study, irrespective of follow-up. Patients who are lost to follow-up will be considered as having had a clinical failure, an adverse outcome and duration of disease equal to the maximum duration measured in the other patients. Patients in whom GPs did not follow the respective algorithm recommendation and/or who did not have complete telephone follow-up will be excluded from the per-protocol analysis.

Primary Analysis

Odds ratio of antibiotic prescription between 2 groups as well as the difference in proportion of patients prescribed an antibiotic by day 28 using logistic regression corrected for variation at the GP level (generalized linear mixed effect)

Secondary Analyses

The following statistical analyses are planned:

- Difference between the mean number of days with restricted activities by day 14 using linear mixed effect regression
- Difference between the mean number of medical consultations by day 28 using linear mixed effect regression
- Odds ratio of adverse outcome between 2 groups as well as the difference in proportion of patients with adverse outcome and clinical failure using logistic regression corrected for variation at the GP level (generalized linear mixed effect)
- Difference between the mean daily symptom scores measured in the different arms. The effects of the interventions on recovery will be studied by comparing the slopes of symptom scores over time between arms
- Difference in the mean duration of total time spent in the practice using linear mixed effect regression
- Difference in levels of satisfaction of providers and of patients between arms
- Difference in the mean cost per arm using linear mixed effect regression
- Diagnostic performance of:
 - individual host biomarker(s) based on crude positive and negative likelihood ratios, and on the area under the curve of receiver operator characteristic (ROC) curves, to predict the development of a life-threatening disease, clinical failure, or the presence of pneumonia (using a clinical diagnosis).

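### With equal true rates of 5%, 210 patients per arm gives about 15–24% power, not 80%, to show non-inferiority on the composite adverse outcome at a 2-point margin

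*Combined protocol and SAP*

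**What the plan says.** Section 11.2 sizes the trial on antibiotic prescription, with "14 GPs and 15 patients per GP in each arm (210 patients per arm and a total of 630 patients") and an intracluster coefficient of 0.06. It then adds two non-inferiority claims in one sentence: "This sample size guarantees a power of 80% to prove non-inferiority in terms of duration of activities restriction" (margin 1 day, standard deviation 4 days), and likewise for the composite adverse outcome, with the probability in the usual care "arm 0.05 with a non-inferiority margin of 0.02". It gives no true rate for the intervention arms, and no one-sided level or intracluster coefficient specific to these endpoints. The only alpha in the section is 5%, attached to the prescribing comparison. The section refers to simulations in Figure 4.

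Section 11.1 makes the safety expectation part of the alternative hypothesis: "no difference in terms of clinical outcome, duration of the episode, activities restrictions and adverse outcomes".

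Section 11.4 plans, among the secondary analyses, the "difference in proportion of patients with adverse outcome and clinical failure using logistic regression corrected for variation at the GP level". It mentions no confidence interval and no comparison with either margin.

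**The concern.** A 2-point margin around a 5% event rate is demanding: about 10 events per arm are expected (210 × 0.05 = 10.5). A trial of this size cannot normally resolve 2 points, so a claim of 80% power needs checking.

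The composite (death, hospital admission, complications) is where harm from withheld antibiotics would appear, and section 3.4 names that as a potential risk of the intervention. If the report finds no significant difference, readers will set it against the stated 80% and take safety as shown. With equal true rates, the real chance of showing non-inferiority is between about one in seven and one in four.

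**Working it through.** **Inputs.** From 11.2: n = 210 per arm (14 GPs × 15 patients), usual-care rate 0.05, margin 0.02 (read as an absolute difference), stated power 80%. From 11.1: no difference in adverse outcomes, hence a true rate of 0.05 in both arms. Sidedness for non-inferiority is not given in the text, so one-sided 2.5% and 5% are both shown. The 0.06 intracluster coefficient (ICC) belongs to prescribing; using it, or 0.01, for other endpoints is an assumption.

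**Composite, no clustering.**

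SE = √(2 × 0.05 × 0.95 / 210) = 0.02127, or 2.13 points.

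Power = Φ(margin/SE − z) = Φ(0.940 − z):
- z = 1.960: 15.4%
- z = 1.645: 24.1%

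Exact binomial enumeration agrees: 16.7% / 25.0% with Wald limits and 14.5% / 22.7% with Newcombe limits.

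**Composite and activity days, with clustering.** The design effect is 1 + 14 × ICC. For days, SE = 4 × √(2/210) = 0.390 day and power = Φ(1/0.390 − z).

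| Assumed ICC | Composite, 2.5% / 5% | Activity days, 2.5% / 5% |
|---|---|---|
| 0 | 15.4% / 24.1% | 72.6% / 82.0% |
| 0.01 | 14.0% / 22.2% | 67.0% / 77.5% |
| 0.06 | 10.3% / 17.1% | 47.2% / 59.6% |

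For activity days the stated 80% is reproduced only at one-sided 5% with clustering ignored or almost absent. The design effect that still leaves 80% is (1/0.390)² / (1.645 + 0.842)² = 1.0615, so the ICC can be at most (1.0615 − 1)/14 = 0.0044. With one-sided 5% and no clustering, the composite has 24%.

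**What would give 80% on the composite.**
- Sample size: n = (z + 0.842)² × 0.095 / 0.0004 = 1,864.1 (one-sided 2.5%) or 1,468.4 (5%), so about 1,865 or 1,469 per arm before clustering.
- Margin at 210 per arm: (z + 0.842) × 0.02127 = 6.0 or 5.3 points.
- Alpha: 1 − Φ(0.940 − 0.842) = 46% one-sided.
- Pooling both intervention arms (210 against 420): only 19.1% or 28.8%.
- True benefit: solving Φ((0.02 + 0.05 − p)/SE − z) = 0.80 for the intervention rate p gives 1.99% (2.5%) or 2.42% (5%), less than half the usual-care rate.

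The probability that the point estimate alone falls below 2 points, with no confidence limit, is Φ(0.940) = 83%. That is close to the stated figure, but it is not a non-inferiority test. Whether the simulations used such a criterion cannot be told from the text.

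**What the data would look like.** Identical observed rates of 5% give an upper bound of 1.960 × 2.13 = 4.2 points or 1.645 × 2.13 = 3.5 points, both above the margin. Against 10 events in 210 usual-care patients, the intervention arm could have at most 6 events (one-sided 2.5%) or 7 (one-sided 5%) for the bound to fall below 2 points. Wald and Newcombe limits agree on these counts.

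**The case against.** The strongest objection is that the simulations behind 11.2 are in Figure 4, which could not be read. They may state a true intervention rate, a one-sided level and an ICC. That stands as a limit: nothing here shows those inputs are absent from the figure. It does not rescue the sentence, which presents 80% without conditions beside inputs that do not yield it. A benefit large enough to yield it would go beyond the no-difference hypothesis of 11.1.

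Second, the activity-days figure is reproducible at one-sided 5% without clustering, a fair reading of the only alpha given. This also stands. The lower days figures are scenarios, not proof of error, and that half of the sentence mainly needs its assumptions stated.

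Third, the composite is a secondary outcome, patient numbers rest on prescribing, and nothing in the plan says non-significance will be read as non-inferiority. True, but 11.2 does claim that non-inferiority can be proved, and 11.4 gives no rule for doing so.

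Fourth, the power also depends on unsettled choices: which pair of arms the margin applies to, which analysis set supports the claim, and how losses count. Section 11.4 counts patients lost to follow-up as adverse outcomes, whereas section 7.2 excludes unreachable patients from the safety analysis. If 5% were lost in each arm (an assumption), the 11.4 rule would raise the rate to 0.05 + 0.95 × 0.05 = 9.75%, and power would fall to about 10% / 17% before clustering. These are refinements, and this one makes the shortfall larger.

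**Conclusion.** The concern holds. On the rate, margin and sample size in 11.2, and with the equal rates implied by 11.1, power for the composite is 15.4% (one-sided 2.5%) or 24.1% (one-sided 5%) before clustering, against a stated 80%. The sample is short by a factor of about nine (1,865/210) or seven (1,469/210). No conventional alpha, pooling of arms or allowance for clustering closes the gap. Only an unstated true benefit, to a rate of about 2.0–2.4%, would.

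The conclusion assumes equal true rates and an absolute margin; the clustered figures rest on assumed ICCs. It does not concern the power for antibiotic prescription. The safety statement must be corrected, because as written it credits the trial with an ability it does not have.

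**What to change.** **Section 11.2.** Replace the non-inferiority sentence with recomputed power for each endpoint. State the one-sided level, the true rates assumed (equal 5%, or the benefit that Figure 4 used, if any), the ICC and the pair of arms.

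**Section 11.4.** Report the planned adverse-outcome risk difference from the GP-level model with a 95% confidence interval. Claim non-inferiority only if the upper bound is below 2 points. A 95% interval corresponds to one-sided 2.5%; if one-sided 5% is chosen, the matching bound comes from a 90% interval. State that a non-significant difference will not be read as non-inferiority. For activity days, compare the upper confidence bound from the mixed model with 1 day. Name the analysis set for these claims, and reconcile the loss-to-follow-up rules in 7.2 and 11.4.

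**Section 11.1.** Reword the no-difference clause to match.

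**Separate minor correction.** The synopsis analyses the "mean number of days with restricted activities by day 7 using linear mixed effect regression", whereas 11.4 has the "mean number of days with restricted activities by day 14 using linear mixed effect regression". Choose one window and match the planning standard deviation to it.

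**Cost.** Protocol wording only, with no extra patients or data. The stated safety power becomes much less favourable, and the trial will probably report an inconclusive adverse-outcome comparison.

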11.3 Statistical criteria of termination of trial

As the risks associated with the intervention can be considered minimal, there are no statistical criteria for terminating the trial. Safety analyses are described below.

11.4 Planned Analyses

Datasets to be analysed, analysis populations

The analysis will be performed in intention to treat (pragmatic trial). The analysis population will comprise all patients included by the randomised GPs. The primary analysis will include all patients enrolled in the study, irrespective of follow-up. Patients who are lost to follow-up will be considered as having had a clinical failure, an adverse outcome and duration of disease equal to the maximum duration measured in the other patients. Patients in whom GPs did not follow the respective algorithm recommendation and/or who did not have complete telephone follow-up will be excluded from the per-protocol analysis.

Primary Analysis

Odds ratio of antibiotic prescription between 2 groups as well as the difference in proportion of patients prescribed an antibiotic by day 28 using logistic regression corrected for variation at the GP level (generalized linear mixed effect)

Secondary Analyses

The following statistical analyses are planned:

- Difference between the mean number of days with restricted activities by day 14 using linear mixed effect regression
- Difference between the mean number of medical consultations by day 28 using linear mixed effect regression
- Odds ratio of adverse outcome between 2 groups as well as the difference in proportion of patients with adverse outcome and clinical failure using logistic regression corrected for variation at the GP level (generalized linear mixed effect)
- Difference between the mean daily symptom scores measured in the different arms. The effects of the interventions on recovery will be studied by comparing the slopes of symptom scores over time between arms
- Difference in the mean duration of total time spent in the practice using linear mixed effect regression
- Difference in levels of satisfaction of providers and of patients between arms
- Difference in the mean cost per arm using linear mixed effect regression
- Diagnostic performance of:
 - individual host biomarker(s) based on crude positive and negative likelihood ratios, and on the area under the curve of receiver operator characteristic (ROC) curves, to predict the development of a life-threatening disease, clinical failure, or the presence of pneumonia (using a clinical diagnosis).
 - combined biomarkers based on sensitivity and specificity generated by classification and regression trees (CART) analyses, to predict the development of a life-threatening disease, clinical failure, or the presence of pneumonia (using a clinical diagnosis).

For each arm of the study, socio-demographic and clinical characteristics will also be described.

Interim analyses

For quality and safety purposes, interim analyses will be performed after inclusion of 50 patients in each of the intervention and control arms. The results of the interim analysis will be reviewed by the steering committee.

Safety analysis

An annual safety analysis will be done by the study coordinator, comparing the incidence of clinical failure by day 7, hospital admissions and deaths between both groups. This will be included in the annual safety report.

Adverse events will be reported to the steering committee within seven days.

Deviation(s) from the original statistical plan

Any deviation from the original statistical plan will be justified and reported in the final study report.

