An individual patient may also choose to refuse the phone interview, without discontinuing the study itself. In this case, the investigators can access the medical file until the end of the 28 days observation period.

There are no foreseeable reasons for investigators to withdraw a patient from the study. Patients who are not reachable during follow-up will not have outcome data. They will be excluded from the analysis of the safety of the intervention but they will still be included in the assessment of impact on antibiotic treatment and of the feasibility of the intervention.

Physicians may choose to discontinue participating in the study. If so, they are responsible of informing the study team. If discontinuation occurs before the training and randomisation session, they will be replaced by another willing physician. If discontinuation occurs after patient recruitment, training and randomisation, patient outcomes will be collected by the study staff until the end of planned follow-up. Access to the medical files will be discussed on a case by case basis with the physician.

There is no foreseeable reason for the investigators to withdraw a physician from the study once he participated in patient recruitment, training and randomisation.

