9.2 Assessments of outcomes

Assessment of primary outcome

Pilot Study

Assessment of the outcomes of the pilot study has been described in section 8.5.1.

Randomized intervention study

Assessment of the outcomes of the randomized intervention study has been described in section 8.5.2.

Assessment of secondary outcomes

Pilot Study

Assessment of the outcomes of the pilot study has been described in section 8.5.1.

Randomized intervention study

Assessment of the outcomes of the randomized intervention study has been described in section 8.5.2.

Assessment of other outcomes of interest

Assessment of the exploratory outcomes has been described in section 8.5.2.3

Assessment of safety outcomes

Adverse events

The GP will be asked to record any serious adverse events (hospitalization, death) within 7 days into the eCRF. Any new recording of severe adverse events (SAE) will be automatically notified to the PI. Adverse events recorded by telephone follow-up will also be recorded

Laboratory parameters

In the intervention arms, prescription of laboratory tests (other than PCT POCT) will be at the discretion of the participating physicians. They will follow their usual routine, either for tests performed in house or sent to an external laboratory. No additional quality control or standard procedures are planned for this aspect.

Vital signs

Vital signs will be assessed with the usual equipment available to the GP at his practice. Measurement is expected to reflect routine practice, and as such no standardized measurement protocol or calibration procedures are planned.

Assessments in participants who prematurely stop the study

Patients will be considered lost to follow-up if telephone interviews were not feasible. A patient may change GP over the course of the study, without this affecting his participation in the study. Phone interviews will continue.

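### Sections 7.2 and 11.4 give opposite rules for patients lost to follow-up in the safety comparison (exclude them, or count them as events), and nothing says which governs

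*Combined protocol and SAP*

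**What the plan says.** Section 7.2, under the criteria for withdrawal, states: "Patients who are not reachable during follow-up will not have outcome data". It continues: "They will be excluded from the analysis of the safety of the intervention". The same sentence keeps these patients for the effect on antibiotic treatment and for feasibility.

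Section 11.4, under the datasets to be analysed, states: "Patients who are lost to follow-up will be considered as having had a clinical failure, an adverse outcome". It also gives them the longest disease duration seen among the other patients. Section 9.2 supplies the definition: "Patients will be considered lost to follow-up if telephone interviews were not feasible".

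Four other statements bear on scope:
- Section 11.4 defines a per-protocol set. Patients managed against the algorithm are left out, and so are those "who did not have complete telephone follow-up will be excluded from the per-protocol analysis".
- The annual safety analysis in 11.4 is described as "comparing the incidence of clinical failure by day 7, hospital admissions and deaths between both groups".
- For quality and safety, "interim analyses will be performed after inclusion of 50 patients in each of the intervention and control arms".
- Section 11.5 expects some loss but gives no rate and names no rule.

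For the composite adverse outcome, section 11.2 plans a non-inferiority comparison with the probability in the usual care "arm 0.05 with a non-inferiority margin of 0.02".

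**The concern.** In one safety comparison, a patient cannot be both left out and counted as an event. Because section 9.2 ties loss to telephone contact, patients lost under 11.4 are essentially those not reachable under 7.2. The endpoints overlap too: clinical failure is imputed by 11.4 and is also part of the annual safety analysis.

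At stake is the evidence that fewer antibiotics do no harm, which section 11.1 makes part of the alternative hypothesis. The planned event rate is low and the margin narrow, so a handful of patients handled one way or the other can move the estimate by as much as the margin. If the rule is not fixed in advance, it could be chosen after the data are seen.

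The interim look is more sensitive because it rests on 50 patients per arm. Section 2.9 lets the principal investigator stop the trial as unsafe on those results, section 11.3 sets no statistical criteria, and section 1.6 provides no data safety monitoring committee.

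Neither rule as written uses outcomes the trial already records. Under section 9.2 the GP enters hospitalisation and death within 7 days in the eCRF; 7.2 would drop such a patient if the telephone call failed. The 11.4 rule would score an event whatever the deterioration-visit form or the diary (both section 8.5) shows.

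**Working it through.** **Inputs from the documents:** 210 patients per arm (14 GPs with 15 patients each), usual-care risk 0.05, margin 0.02, ICC 0.06 (section 11.2); 50 per arm at the interim analysis (section 11.4).

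**Assumptions:** all loss rates; all event counts; loss unrelated to outcome; a one-sided 2.5% level for non-inferiority (none is stated); use of the ICC of 0.06, planned for prescribing, for the safety outcome.

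**1. The plan's own figure.** Section 11.2 states 80% power for the composite. With equal risks of 0.05, SE = √(2 × 0.05 × 0.95 / 210) = 0.0213, and power = Φ(0.02/0.0213 − 1.96) = 15% before clustering (24% at one-sided 5%). The design effect 1 + 14 × 0.06 = 1.84 lowers these to 10% and 17%. The 80% is not reproduced. The simulation figure is not shown and the intervention-arm risk is not stated. That is a separate matter, and nothing below depends on it.

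**2. The two rules.** Let p be the risk in patients reached and L the share lost. The 7.2 rule analyses p. The 11.4 rule analyses r = L + (1 − L)p.

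**3. Equal true risk, unequal loss.** With p = 0.05 in both arms the 7.2 difference is 0 and the odds ratio 1.00 throughout. Under 11.4 (intervention minus usual care):
- loss 5% usual care v 5% intervention: difference 0, OR 1.00
- 5% v 7%: +1.9 points, OR 1.22
- 5% v 10%: +4.75 points, OR 1.57
- 10% v 5%: −4.75 points, OR 0.64

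The shift is 0.95 × the gap in L. It equals the margin when the gap is 0.02/0.95 = 0.021, and 0.021 × 210 = 4.4 patients. At the interim analysis, one extra lost patient in an arm shifts the difference by 0.95/50 = 1.9 points.

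**4. Unequal true risk, equal loss.** Take 7% v 5% with 10% lost in each arm.
- 7.2: difference 2.0 points; OR (0.07/0.93)/(0.05/0.95) = 1.43
- 11.4: r = 0.163 v 0.145; difference 1.8 points; OR (0.163/0.837)/(0.145/0.855) = 1.15

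The difference barely moves, but the odds ratio, which 11.4 lists first, is pulled towards 1.

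**5. One invented data set, both rules.** Lost: 10 UltraPro v 15 usual care. Events among those reached: 14 v 10.
- 7.2: 14/200 = 7.0% v 10/195 = 5.1%; +1.9 points, SE 2.4, upper 95% limit 6.6
- 11.4: 24/210 = 11.4% v 25/210 = 11.9%; −0.5 points, SE 3.1, upper 95% limit 5.7

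The estimate changes sign. The upper limit, ignoring clustering, exceeds 2 points under both rules.

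**6. False non-inferiority.** Take a true 7% v 5%, with loss 5.0% in the intervention arm and 7.1% in usual care. Under 7.2 the probability of declaring non-inferiority is 2.5% by construction. Under 11.4, r = 0.1165 v 0.1175, difference −0.0009, SE 0.0314, and Φ((0.02 + 0.0009)/0.0314 − 1.96) = 9.8% (7.1% with the design effect). At one-sided 5% the pair is 5% v 16.4%. With equal 10% loss, 11.4 gives 2.9%.

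**The case against.** The best defence is that the two rules have different scopes. Section 7.2 may mean only the annual safety analysis, a monitoring report that could reasonably use observed cases, while 11.4 governs the intention-to-treat comparison. The defect would then be missing scope wording. This is a plausible intention, but 7.2 is not limited in that way, and the annual analysis includes clinical failure, which 11.4 imputes. Nor does the per-protocol set settle it: 7.2 does not confine its exclusion to that set, which also drops patients managed against the algorithm and so does not isolate loss.

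Several limits on the consequence do stand. Follow-up is the same in all arms (section 3.3) and callers are blinded (section 8.5), which limits unequal calling effort, though not unequal patient response. Section 11.4 lists no formal non-inferiority test. With power as low as in step 1, non-inferiority would usually fail under either rule.

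Some stronger readings are tempting but unsupported. A reader might infer that the safety result will be biased or that harm will be hidden; the documents give no loss rate and no sign of differential loss. A reader might infer that 11.4 misclassifies GP-recorded admissions and deaths; those are events, so 11.4 scores them correctly and it is 7.2 that would lose them. A reader might extend 11.4 to patients who refuse the interview; section 7.2 treats refusal separately from being unreachable.

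**Conclusion.** The point holds. For essentially the same patients, 7.2 prescribes exclusion and 11.4 prescribes counting an event, and no section sets precedence for the secondary safety comparison, the interim analysis or the annual safety analysis. This should be fixed, but it does not reach the primary antibiotic analysis.

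The size is conditional. At an assumed 5% risk with loss unrelated to outcome, a 2.1-point gap in loss moves the 11.4 difference by the full 2-point margin, in either direction: more loss in usual care makes the intervention look safer, more loss in an intervention arm makes it look harmful. The false non-inferiority figures also rest on the assumed one-sided 2.5% level, and their clustered version on the borrowed ICC.

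Neither rule is safe in general. Observed-outcome analysis is biased if loss is related to outcome. Counting lost patients as failures is biased if loss differs between arms, and dilutes the odds ratio even when it does not.

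**What to change.** Make 7.2 and 11.4 agree:
- Prespecify one rule, observed outcomes or lost counted as failure, as main for the safety comparison, and the other as a sensitivity analysis. Which is main is the sponsor's choice.
- State which rule the interim and annual safety analyses follow.
- Before treating an outcome as missing, count a GP-recorded admission or death as an event. The absence of such a record does not show that no event occurred. The diary has an item for shortness of breath but none for fever, so it informs day-7 clinical failure only in part.
- Report loss to follow-up by arm.

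The cost is protocol wording and one extra analysis. No new patients or visits are needed.
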